phase 2 open label study of patients with advanced stage lung cancer treated in the second or third line setting with plinabulin and nivolumab.

Endpoints

5.1.1 Primary endpoints.

- For the initial phase. To determine the safety and tolerability of the combination of nivolumab and plinabulin.
- For the subsequent phase, To evaluate the overall response rate, defined as the sum of complete and partial responses according to RECIST 1.1 criteria, of patients treated with a combination of plinabulin and nivolumab.

5.1.2 Secondary endpoints.

- Evaluate disease control rate, defined as the proportion of patients with CR, PR and SD for more than 8 weeks while on combination plinabulin and nivolumab.
- Evaluate duration of response (DOR), Progression Free Survival (PFS) and Overall Survival (OS)
- Determine the safety and tolerability of the combination of nivolumab and plinabulin.

Dose rationale

Plinabulin has been studied as a single agent in a dose escalation study, the maximum tolerated dose was not reached and the recommended phase 2 dose was 30mg/m². A subsequent phase 1 study using plinabulin with docetaxel showed that plinabulin did not contribute to the toxicity of docetaxel⁹. In this study the initial phase will start with a dose of plinabulin of 20 mg/m² and nivolumab at a flat dose of 240mg. If no dose limiting toxicities (DLTs) are seen the dose of plinabulin will be escalated to 30 mg/m²

Treatment plan

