5.1.4 Second Phase

In the second phase of the study patients will receive plinabulin at the MTD identified previously and nivolumab 240 mg on the same day and repeated every 2 weeks. Re-staging studies will be conducted every 8 (+/-1) weeks, after cycle seven scans will be done every 12 (+/-1) weeks. Those who achieve a complete response, partial response, or stable disease will continue on study. Will use RECIST 1.1 criteria to determine response to treatment. Patients with progressive symptomatology and progressive disease seen in imaging studies will be taken off study. To account for pseudo-progression, in the case of progressive disease in the absence of worsening symptomatology, at the discretion of the treating physician, a patient will be allowed to continue receiving treatment for 2 more cycles followed by restaging studies. If progressive disease is confirmed the patient will be taken off study.

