6.0 STUDY CONDUCT AND TRIAL PROCEDURES

Prior to undergoing any study-specific procedure, patients must read and sign the current Institutional Review Board (IRB)-approved informed consent form. Procedures conducted as part of the subject's routine clinical management (e.g., blood count, imaging study) and obtained prior to signing of informed consent may be utilized for screening or baseline purposes provided these procedures are conducted as specified in the protocol.

Screening

Diagnostic or laboratory studies performed exclusively to determine eligibility for this trial must only be done after obtaining written informed consent. Documentation of the informed consent will be maintained in the patient's chart.

Studies or procedures that were performed per standard of care prior to signing the consent form may be used for baseline values if they fall within the screening specified window (see table 6.10).

The screening visit will occur up to 28 days prior to initiating study treatment. The following should be obtained, [see table 6.10](#).

- Medical History
 - Histologic type of lung cancer diagnosis
 - Prior NSCLC treatment history
 - Medical History
 - Subject demographics
- Physical examination
 - Examination of major organ systems
 - ECOG performance status
 - Height, weight, and vital signs (temperature, blood pressure, heart rate, and respiratory rate),
- Laboratory Evaluations should include:
 - CBC with differential
 - Serum chemistry (sodium, potassium, chloride, carbon dioxide, creatinine, BUN, glucose, calcium, albumin, total bilirubin, AST, ALT, total protein, and alkaline phosphatase)
 - Thyroid function (TSH, T3, Free T4)
 - Pregnancy test (serum or urine) for all women of childbearing potential
- CT scan of known sites of involvement (a prior CT scan that is no more than 28 days before the initiation of treatment may be used).
- Brain MRI or CT (prior MRI or CT scan that is no more than 28 days before the initiation of treatment may be used).

Biopsy

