6.6 Tumor Evaluations

CT scan of all known areas of disease with tumor evaluation using RECIST 1.1 and IrRC criteria will be performed every 8 (+/-1) weeks. After 7 cycles of therapy, imaging studies will be performed every 12 (+/- 1) weeks.

- Patients who have a CR, PR, or SD may continue on study per study protocol.
- If progressive disease is documented the patient may remain on study provided:
 - The patient does not have clinical signs or symptoms of tumor progression
 - No decline in ECOG performance status
 - Absence of progressive tumor at critical anatomic sites (i.e. spinal cord compression).
 - Treating physician believes that the patient continues to derive clinical benefit from study treatment
 - Repeat imaging scans should be repeated ≥ 4 weeks (+/- 7 days) after documented progression. If progression is confirmed the subject will be removed from study.

Off Study Visit.

Patients will undergo the following assessments 28 days (+/- 14 days) after last dose of study treatment

- History and physical examination that includes examination of major organ systems, ECOG performance status, weight, vital signs, adverse events assessment
- Laboratory evaluations including:
 - CBC with differential
 - Blood chemistry (sodium, potassium, chloride, carbon dioxide, creatinine, BUN, glucose, calcium, albumin, bilirubin, AST, ALT, total protein, and alkaline phosphatase)

Permitted medications

All treatments that the investigator considers necessary for a subject's welfare may be administered at the discretion of the

investigator in keeping with the community standards of medical care.

If an increase in systolic blood pressure to > 160 mmHg is observed after administration of plinabulin, oral amlodipine 10 mg or an equivalent calcium channel blocker should be administered before each subsequent dose. Increases in systolic blood pressure above 200 mmHg should be managed with nitroprusside or similar regimen per institutional practice.

Dexamethasone may be used as either a pre-medication or as a rescue medication for patients that experience plinabulin-related nausea and vomiting that is not controlled adequately with a 5HT3 agonist (e.g. ondansetron) alone

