The study population for analyses will include all patients enrolled in the study who receive treatment at the MTD and receive at least one dose of study medication. The primary endpoint will be overall response rate. As noted above, 11 or more observed responses among 33 patients would be considered potentially efficacious and would justify further study. Responses include both complete and partial responses, as defined by RECIST 1.1 criteria. The disease control rate (DCR), defined as the stable disease + partial response rate will be calculated. Toxicity rates will be described as the overall percentage of patients experiencing Grade 3 or higher toxicity.

9.3 Time to event definitions.

Progression free survival is defined as the time from registration until objective tumor progression or death due to any cause, whichever comes first. The date of disease progression will be defined as the earliest date of radiological disease progression as assessed by the investigator using RECIST 1.1 criteria, or clinical disease progression. For patients who have not progressed or died at the time of the analysis, censoring will be performed using the date of the last adequate disease assessment.

Overall survival is defined as the time from registration until the date of death due to any cause. Patients last known to be alive at the time of the analysis will be censored at the date of last contact.

Duration of response is defined as the time between receipt of first study drug and until the date of progression.

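### Duration of response is timed from the first dose of study drug, not from the first response, so it includes each responder's time to response; death and censoring are not stated for it

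*Combined protocol and SAP*

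**What the plan says.** Section 5.1.2 lists duration of response (DOR) as a secondary endpoint beside PFS and overall survival (OS). Its only definition is in section 9.3, Time to event definitions: "Duration of response is defined as the time between receipt of first study drug and until the date of progression". The trial objectives and endpoint lists name DOR without defining it.

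The same section treats the other two time-to-event endpoints more fully:

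- **PFS.** "Progression free survival is defined as the time from registration until objective tumor progression or death due to any cause". The progression date is the earliest radiological progression judged by the investigator "using RECIST 1.1 criteria, or clinical disease progression". The paragraph ends with a censoring rule: "For patients who have not progressed or died at the time of the analysis, censoring will be performed" at the last adequate disease assessment.
- **OS.** It runs from registration to death and is censored at last contact.

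Section 9.2 defines a response as complete or partial (CR or PR) by RECIST 1.1. The scan schedule is in section 5.1.4, "Re-staging studies will be conducted every 8 (+/-1) weeks", and again in section 6.6. Both lengthen the interval to 12 weeks after cycle 7.

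**The concern.** A duration of response should say how long a response lasted once it was obtained. Here the clock starts at first dose, and the date of first CR or PR appears nowhere in the definition. The sentence does not even restrict the endpoint to responders, although its name implies that.

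Two consequences follow. First, the time a responder took to respond is counted as time in response, so a late responder gains more than an early one. Second, DOR and PFS end on the same date for a responder who progresses, so DOR adds little to PFS. A reader who sees the usual label would take the figure for something it is not, and could wrongly compare it with durations timed from response.

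A smaller gap concerns the end of the clock. The sentence names only progression. It does not say how to treat a responder who dies with neither radiological nor clinical progression, or one who is progression-free at the analysis.

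**Working it through.** The documents give no DOR figure to reproduce, so the check is an identity followed by its size under the plan's scan schedule.

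**Identity.** For a responder who progresses, let R be registration, D first dose, C first documented CR or PR, and P progression.

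- DOR as written = P − D = (C − D) + (P − C). The excess over a duration timed from response is C − D, the time to response.
- PFS = P − R, so DOR as written = PFS − (D − R).

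The gap D − R is not fixed by the documents. Section 6.0 says "The screening visit will occur up to 28 days prior to initiating study treatment". If registration falls inside that window (an assumption), DOR and PFS differ by at most 28 days in a progressing responder.

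**Time added.** The input is the 8 (+/-1) week schedule of sections 5.1.4 and 6.6. Assumptions: scans are timed from about first dose, and no unscheduled scan comes earlier. Months = weeks × 7 / 30.4375.

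| Response first seen at | Weeks added | Months added |
|---|---|---|
| Scan 1 | 7, 8, 9 | 1.61, 1.84, 2.07 |
| Scan 2 | 15, 16, 17 | 3.45, 3.68, 3.91 |

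If the one-week tolerance applies to each interval in turn, scan 2 can fall at 14 to 18 weeks: 14 × 7 / 30.4375 = 3.2 months and 18 × 7 / 30.4375 = 4.1 months.

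**Mean over responders**, for an assumed share first seen at scan 1 and the rest at scan 2:

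- 100%: 1.84 months
- 75%: 0.75 × 1.84 + 0.25 × 3.68 = 2.30 months
- 50%: 0.50 × 1.84 + 0.50 × 3.68 = 2.76 months

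**Single responders**, the two definitions compared:

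| Response (week) | Progression (week) | As written (weeks) | From response (weeks) | Ratio |
|---|---|---|---|---|
| 8 | 16 | 16 | 8 | 2.0 |
| 8 | 24 | 24 | 16 | 1.5 |
| 8 | 32 | 32 | 24 | 1.33 |
| 16 | 24 | 24 | 8 | 3.0 |

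**Longer responses.** The relative effect shrinks as responses lengthen. With response at week 7 to 9 and an assumed duration from response:

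- 1.5 months becomes 3.1 to 3.6 (+107% to +138%)
- 6 months becomes 7.6 to 8.1 (+27% to +34%)
- 12.7 months becomes 14.3 to 14.8 (+13% to +16%)

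The values 1.5 and 12.7 months are the DOR figures that the background section cites from the earlier docetaxel study. They are used for scale only, since the protocol does not say how that study defined DOR.

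**Death and censoring.** Within section 9.3, PFS has death as an event and a censoring rule, and OS has its own censoring rule. The DOR sentence has neither. Clinical progression counts in the progression date given for PFS; if that date is used for DOR too, only deaths with neither kind of progression are uncovered. The documents give no basis for sizing this.

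**The case against.** Five points can be made for the plan.

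1. **The censoring rule may already cover DOR.** The sentence sits under a heading common to all time-to-event endpoints and does not itself name PFS. OS needs a separate rule because it ends in death. This reading is reasonable, so the fair statement is that censoring is not stated explicitly for DOR. Even so, death remains unnamed as a DOR event and the start of the clock is unchanged.

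2. **The size rests on assumptions.** The documents fix neither the scan anchor nor the times to response, and they do not define registration. This stands; the figures are a range. The direction does not depend on them: the excess equals the time to response and cannot be negative.

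3. **The large ratios come from short responses.** This is correct. For a 12.7-month duration the increase is 13% to 16%.

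4. **Timing from first documented response is also a convention.** A response first seen at week 8 began at some unknown earlier time. The ratios therefore compare two definitions and do not measure error against a known truth. That does not make first dose a sensible start for a response.

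5. **Little depends on it.** The trial has a single arm, and its hypothesis and decision rule concern response rate only. Among 33 patients the expected number of responders is 33 × 0.20 = 6.6 to 33 × 0.40 = 13.2, so DOR will be descriptive in a small group. The start point is openly stated, and the results can be re-timed later from the same scan dates. This limits the severity but leaves the definition wrong.

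**Conclusion.** The concern holds. As written, DOR does not measure how long responses last. It lengthens every responder's value by the time to response and, in those who progress, equals PFS less the interval from registration to first dose.

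Under the assumed scan anchor, the addition is 1.6 to 2.1 months for responses first seen at scan 1 and about 3.7 months at scan 2. On the assumed splits between the two scans, the mean is 1.8 to 2.8 months. The missing statements on death and censoring are a secondary clarification of unknown size.

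This should be corrected, but it is confined to a descriptive secondary endpoint. The response rate, sample size, error rates and decision rule do not change.

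**What to change.** Replace the DOR sentence in section 9.3 with:

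> Duration of response, in patients with CR or PR, is the time from the first documented CR or PR (RECIST 1.1) to first documented progression or death from any cause, whichever is first; patients with neither are censored at the last adequate disease assessment.

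The criterion should be named because section 6.6 plans "tumor evaluation using RECIST 1.1 and IrRC criteria will be performed every 8 (+/-1) weeks", while the response endpoint uses RECIST 1.1 alone. Progression should carry the same date as in PFS.

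The cost is one sentence. The scan, progression and death dates are already needed for response rate, PFS and OS, and no visit, procedure or sample size changes. The reported DOR will be shorter.
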